11.7.2. Handling of Missing Data

Element	Reporting Detail
General	
 • Missing data occurs when any requested data is not provided, leading to blank fields on the collection instrument : 
 ○ These data will be indicated by the use of a “blank” in subject listing displays. Unless all data for a specific visit are missing in which case the data is excluded from the table. ○ Answers such as “Not applicable” and “Not evaluable” are not considered to be missing data and should be displayed as such.
Outliers	
 • Any subjects excluded from the summaries and/or statistical analyses will be documented along with the reason for exclusion in the clinical study report.

11.7.2.1. Handling of Missing Dates

Element	Reporting Detail
General	Partial dates will be displayed as captured in subject listing displays.
Adverse Events	
 • The eCRF allows for the possibility of partial dates (i.e., only month and year) to be recorded for AE start and end dates; that is, the day of the month may be missing. In such a case, the following conventions will be applied for calculating the time to onset and the duration of the event: 
 ○ Missing Start Day: First of the month will be used unless this is before the start date of study treatment; in this case the study treatment start date will be used and hence the event is considered On-treatment as per Appendix 4: Treatment States and Phases. ○ Missing Stop Day: Last day of the month will be used, unless this is after the stop date of study treatment; in this case the study treatment stop date will be used.

Element	Reporting Detail
	
 • Completely missing start or end dates will remain missing, with no imputation applied. Consequently, time to onset and duration of such events will be missing. • Start or end dates which are completely missing (i.e. no year specified) will remain missing, with no imputation applied.

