7.4.1.1. Time period and Frequency for collecting AE and SAE information

- Any SAEs assessed as related to study participation (e.g., protocol-mandated procedures, invasive tests, or change in existing therapy) or related to a GSK product will be recorded from the time a subject consents to participate in the study up to and including any follow-up contact.
- AEs will be collected from the start of the run-in period (Day -7) until the follow-up contact (see Section 7.4.1.3), at the time-points specified in the Time and Events Table (Section 7.1).
- Medical occurrences that begin prior to the start of study treatment but after obtaining informed consent may be recorded on the Medical History/Current Medical Conditions section of the CRF.
- All SAEs will be recorded and reported to GSK within 24 hours, as indicated in [Appendix 2](#).
- Investigators are not obligated to actively seek AEs or SAEs in former study subjects. However, if the investigator learns of any SAE, including a death, at any time after a subject has been discharged from the study, and he/she considers the event reasonably related to the study treatment or study participation, the investigator must promptly notify GSK.

NOTE: The method of recording, evaluating and assessing causality of AEs and SAEs plus procedures for completing and transmitting SAE reports to GSK are provided in [Appendix 2](#).

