11.4. Appendix 4: Treatment States and Phases

11.4.1. Treatment States for AE Data

Treatment State	Definition
Pre-Treatment	AE Start Date < Study Treatment Start Date
On-Treatment	If AE onset date is on or after treatment start date & on or before treatment stop date. Study Treatment Start Date ≤ AE Start Date ≤ Study Treatment Stop Date [+ Lag Time]
Post-Treatment	If AE onset date is after the treatment stop date. AE Start Date > Study Treatment Stop Date
Onset Time Since 1 st Dose (Days)	If Treatment Start Date > AE Onset Date = AE Onset Date - Treatment Start Date If Treatment Start Date ≤ AE Onset Date = AE Onset Date - Treatment Start Date +1 Missing otherwise.
Duration (Days)	AE Resolution Date – AE Onset Date + 1
Drug-related	If relationship is marked 'YES' on [Inform/CRF OR value is missing].

NOTES:

- If the study treatment stop date is missing then the AE will be considered to be On-Treatment.

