11.7.2.2. Handling of Partial Dates

Element	Reporting Detail
Concomitant Medications	
 • Partial dates for any concomitant medications recorded in the CRF will be imputed using the following convention: 
 ○ If the partial date is a start date, a '01' will be used for the day and 'Jan' will be used for the month ○ If the partial date is a stop date, a '28/29/30/31' will be used for the day (dependent on the month and year) and 'Dec' will be used for the month. • The recorded partial date will be displayed in listings.
Adverse Events	
 • Any partial dates for adverse events will be raised to data management. If the full date cannot be ascertained, the following assumptions will be made: 
 ○ If the partial date is a start date, a '01' will be used for the day and 'Jan' will be used for the month. ○ However, if these results in a date prior to Week 1 Day 1 and the event could possibly have occurred during treatment from the partial information, then the Week 1 Day 1 date will be assumed to be the start date. ○ The AE will then be considered to start on-treatment (worst case). ○ If the partial date is a stop date, a '28/29/30/31' will be used for the day (dependent on the month and year) and 'Dec' will be used for the month. • The recorded partial date will be displayed in listings.

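### The SAP has two unreconciled rules for partial AE dates, and one gives a zero or negative duration to any post-dose AE whose stop day is missing

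*SAP*

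**What the plan says.** SAP 11.7.2.1 expects partial dates: "The eCRF allows for the possibility of partial dates (i.e., only month and year) to be recorded for AE start and end dates". For those, "the following conventions will be applied for calculating the time to onset and the duration of the event". A missing start day becomes the first of the month, with the study treatment start date as a floor: "First of the month will be used unless this is before the start date of study treatment". A missing stop day becomes the last of the month, "unless this is after the stop date of study treatment; in this case the study treatment stop date will be used".

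SAP 11.7.2.2 covers partial AE dates again. It first sends them to data management, and imputes only when the full date cannot be obtained. A start date then takes day 01 and month January. If that falls before dosing and the event could have occurred on treatment, "then the Week 1 Day 1 date will be assumed to be the start date". A stop date takes the last day of the month and December, with no reference to the end of treatment. Neither section mentions the other.

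SAP 11.4.1 computes duration as "AE Resolution Date – AE Onset Date + 1" and has a post-treatment state for AEs with onset after the treatment stop date. It refers to a single treatment start and stop date, with no period-level version. Protocol 7.4.1.1 states that "AEs will be collected from the start of the run-in period (Day -7) until the follow-up contact".

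**The concern.** This study exists to observe what happens after dosing stops, so post-dose AEs are expected by design. A rule that cuts the AE stop date back to the last dose cannot suit an AE that began after it: the imputed stop precedes the onset.

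The second rule gives a different answer for the same record, and a programmer would have to choose between them. Both rules also anchor start dates to one date, while each subject has two first doses on two different treatments. Week 1 Day 1 is not a label in this study's schedule, which numbers days within each period. At stake are the derived duration of a partially dated AE and the period, hence possibly the treatment, to which it is attributed.

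**Working it through.** **Inputs.** Nominal last dose on Day 14 (±2 days) and 21 days of monitoring to Day 35 in each period (Protocol 4.2, SAP 2.3). Follow-up up to Day 42, after Period 2 only (Protocol 7.1). Duration formula from SAP 11.4.1. Shortest interval from Period 1 Day 1 to Period 2 Day 1: 34 days when Period 1 Day 35 doubles as Period 2 Day 1 (Protocol 4.2), or 32 days if dosing is two days shorter. The documents give no count of partial dates, so the effect can be sized per case only. The plan states no figure to reproduce. Calendar shares below assume every possible Day 1 date in 2016 and equally likely onset days.

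**1. Duration under 11.7.2.1.** For an onset after the last dose, the end of the stop month is always later than the last dose, so the cap always applies. Duration = 14 − s + 1.

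| Onset day s | 15 | 16 | 21 | 35 | 42 |
|---|---|---|---|---|---|
| Duration (days) | 0 | −1 | −6 | −20 | −27 |

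If the last dose is on Day D instead, the result is D − s + 1, still 0 on the next day.

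If the start day is missing too, the start becomes the first of the month. The duration is then 0 or less only when that date falls after the last dose, that is, when the onset's day of the month is at most s − 14. Over s = 15 to 35 this is 12 × (1 + … + 21) = 12 × 231 = 2,772 of 366 × 21 = 7,686 cases, or 36%.

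**2. The two stop-date rules on one record.** Period 1 Day 1 is 1 March 2016, Period 2 Day 1 is 4 April and the last dose is 17 April. The AE starts on 25 April and its stop is recorded as April 2016.

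- 11.7.2.1: stop = 17 April; 17 − 25 + 1 = −7 days.
- 11.7.2.2, recorded month kept: stop = 30 April; 30 − 25 + 1 = 6 days.
- 11.7.2.2, December imposed: stop = 31 December; 251 days.

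The sections disagree on either reading of 11.7.2.2.

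**3. Start date of a Period 2 AE.** Same subject, with the AE start recorded as April 2016.

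- 11.7.2.1, floor at the first dose of the study: 1 April. This is Period 1 Day 32, three days before Period 2 Day 1.
- 11.7.2.1, floor at the period's first dose: 4 April.
- 11.7.2.2, recorded month kept: 1 April, or 4 April if Week 1 Day 1 means Period 2 Day 1.
- 11.7.2.2, January imposed and Week 1 Day 1 taken as the first dose of the study: 1 January, reset to 1 March, which is Period 1 Day 1.

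With the first of the recorded month and a study-level floor, about 42% of Period 2 onsets on Days 1 to 35 land before Period 2 Day 1. Between 0 and 7% land within Period 1 Days 1 to 14 (6.75% at a 32-day interval, 4.7% at 34 days, 0 at 62 days or more). None reaches Period 1 Day 1: the first of the month is at most 30 days before onset, and Period 1 Day 1 is at least 32 days before it.

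**4. Consistency of readings.** If treatment start and stop are both read per period, the duration defect applies in both periods and the start-date shift disappears. If both are read once per study, the shift remains and the duration defect applies only after the last Period 2 dose. No single reading gives both effects at full size.

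**The case against.** A reader might infer that every AE after the last dose gets an impossible duration, since 21 of each period's 35 days (60%) are post-dose. The documents do not support that. The stop day must also be missing, and 60% is a share of calendar time, not of AEs.

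A reader might also infer that Period 2 AEs are moved to Period 1 Day 1 and counted against the wrong treatment. That needs January to overwrite a recorded month (or the month to be missing) and Week 1 Day 1 to mean the first dose of the study. On that reading 78% to 87% of partially dated Period 2 onsets would land there. But 11.7.2.2 chooses among 28, 29, 30 and 31 according to the month and year, which would be pointless if every stop fell in December. That suggests a recorded month is kept. SAP 11.7.2.1 also describes month and year as known. Nor does the SAP say that AEs are assigned to treatment by imputed date.

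Further points reduce the consequence, and they stand:

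- Partial dates are queried with data management before any imputation.
- A second diary card is issued for Period 2 (Protocol 7.1), which helps separate AEs by period at source.
- Treatment state depends on the AE start date only, so the stop-date cap cannot change AE counts.
- Safety Tables 3.1 to 3.3 do not summarise duration, and listings show partial dates as recorded.

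What the objection does not remove is the cap itself, the unresolved conflict between the two stop-date rules, the undefined Week 1 Day 1, and a start-date floor not stated per period.

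**Conclusion.** Wrong as written, with small consequences. The zero or negative duration is certain for a known post-dose onset with a missing stop day; how far it extends depends on whether the stop date is per period or per study. The conflict between the stop-date rules holds on any reading. Imputation of a Period 2 AE to a date before Period 2 Day 1 is possible because the floor is not period-specific, but a move to Period 1 Day 1 is not established.

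Only AEs whose partial dates cannot be resolved are touched. With about 28 subjects enrolled these are probably few, though the documents give no number. The effect is confined to AE onset, duration and possibly period attribution. The primary and secondary FeNO analyses do not use these dates. Low priority.

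**What to change.** Replace the AE rules in SAP 11.7.2.1 and 11.7.2.2 with one rule:

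- **Missing stop day:** the earlier of the end of the recorded month and the last study contact, never before onset. Remove the treatment-stop cap.
- **Missing start day:** the first of the recorded month. Move it to the first dose date of the relevant period only if that is later and the partial date and other evidence (period diary card, visit, AE stop date) allow onset on or after that dose. An unconditional floor would turn run-in or washout AEs into on-treatment ones.
- **Month:** use January or December only when the month is missing.
- **Label:** replace Week 1 Day 1 with Day 1 of the relevant treatment period.
- **Attribution:** assign each AE to the treatment of the period in which onset occurred, using diary card or visit information when the imputed date is ambiguous. Do not use the visit at which it was reported: Period 1 Day 35 can be combined with Period 2 Day 1, so a Period 1 washout AE reported there could be given to the other treatment.

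Keep the existing query to data management as the first step. The cost is SAP wording, to be settled before unblinding.

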11.7.2.2. Handling of Partial Dates

Element	Reporting Detail
Concomitant Medications	
 • Partial dates for any concomitant medications recorded in the CRF will be imputed using the following convention: 
 ○ If the partial date is a start date, a '01' will be used for the day and 'Jan' will be used for the month ○ If the partial date is a stop date, a '28/29/30/31' will be used for the day (dependent on the month and year) and 'Dec' will be used for the month. • The recorded partial date will be displayed in listings.
Adverse Events	
 • Any partial dates for adverse events will be raised to data management. If the full date cannot be ascertained, the following assumptions will be made: 
 ○ If the partial date is a start date, a '01' will be used for the day and 'Jan' will be used for the month. ○ However, if these results in a date prior to Week 1 Day 1 and the event could possibly have occurred during treatment from the partial information, then the Week 1 Day 1 date will be assumed to be the start date. ○ The AE will then be considered to start on-treatment (worst case). ○ If the partial date is a stop date, a '28/29/30/31' will be used for the day (dependent on the month and year) and 'Dec' will be used for the month. • The recorded partial date will be displayed in listings.

11.7.2.3. Handling of Missing Data for Statistical Analysis

Element	Reporting Detail
Outliers	
 • Any subjects excluded from the summaries and/or statistical analyses will be documented along with the reason for exclusion in the clinical study report.

11.8. Appendix 8: Model Checking and Diagnostics for Statistical Analyses

11.8.1. Statistical Analysis Assumptions

Endpoint(s)	
 • Log_e (FeNO) and FEV1
Analysis	
 • MMRM

 • Model assumptions will be applied, but appropriate adjustments maybe made based on the data. • The Kenward and Roger method for approximating the denominator degrees of freedom and correcting for bias in the estimated variance-covariance of the fixed effects will be used. • An unstructured covariance structure for the R matrix will be used by specifying ‘type=UN’ on the REPEATED line. 
 ○ In the event that this model fails to converge, alternative correlation structures may be considered such as CSH or CS. ○ Akaike's Information Criteria (AIC) will be used to assist with the selection of covariance structure. • Distributional assumptions underlying the model used for analysis will be examined by obtaining a normal probability plot of the residuals and a plot of the residuals versus the fitted values (i.e. checking the normality assumption and constant variance assumption of the model respectively) to gain confidence that the model assumptions are reasonable. • If there are any departures from the distributional assumptions, alternative models will be explored using appropriate transformed data. 	

11.9. Appendix 9 – Abbreviations & Trade Marks

11.9.1. Abbreviations

Abbreviation	Description
AE	Adverse Event
AIC	Akaike's Information Criteria
A&R	Analysis and Reporting
CI	Confidence Interval
CS	Clinical Statistics
CSR	Clinical Study Report
CTR	Clinical Trial Register
CV _b / CV _w	Coefficient of Variation (Between) / Coefficient of Variation (Within)
DOB	Date of Birth
DP	Decimal Places
eCRF	Electronic Case Record Form
IA	Interim Analysis
ICH	International Conference on Harmonisation
IDMC	Independent Data Monitoring Committee
IDSL	Integrated Data Standards Library
IMMS	International Modules Management System
IP	Investigational Product
GUI	Guidance
MMRM	Mixed Model Repeated Measures
PD	Pharmacodynamic
PDMP	Protocol Deviation Management Plan
PK	Pharmacokinetic
PP	Per Protocol
QC	Quality Control
RAP	Reporting & Analysis Plan
RAMOS	Randomization & Medication Ordering System
SAC	Statistical Analysis Complete
SOP	Standard Operation Procedure
TA	Therapeutic Area
TFL	Tables, Figures & Listings
GSK	GlaxoSmithKline

11.9.2. Trademarks

Trademarks of the GlaxoSmithKline Group of Companies
HARP

Trademarks not owned by the GlaxoSmithKline Group of Companies
SAS

11.10. Appendix 10: List of Data Displays

11.10.1. Data Display Numbering

The following numbering will be applied for RAP generated displays:

Section	Tables	Figures
Study Population	1.1 to 1.10	-
Pharmacodynamic	2.1 to 2.8	2.1 to 2.6
Safety	3.1 to 3.3	
Biomarker	4.1 to 4.2	4.1
Section	Listings	
ICH Listings	1 to 18	
Other Listings	19 to 25	

11.10.2. Mock Example Shell Referencing

Non IDSL specifications will be referenced as indicated and if required an example mock-up displays provided in [Appendix 11: Example Mock Shells for Data Displays](#).

Section	Figure	Table	Listing
Study Population	N/A	POP_Tn	POP_Ln
Pharmacodynamic/Biomarker	PD_Fn	PD_Tn	PD_Ln
Safety	N/A	SAFE_Tn	SAFE_Ln

NOTES:

- Non-Standard displays are indicated in the ‘IDSL / TST ID / Example Shell’ or ‘Programming Notes’ column as ‘[Non-Standard] + Reference.’

11.10.3. Deliverable [Priority]

Delivery Priority	Description
Headline [1]	Headline Results
SAC [2]	Final Statistical Analysis Complete

11.10.4. Study Population Tables

Study Population Tables					
No.	Population	IDSL / Example Shell	Title	Programming Notes	Deliverable [Priority]
Subject Disposition					
1.1.	All Subjects	ES1A	Summary of Subject Disposition for the Subject Conclusion Record		Headline [1] SAC [2]
1.2.	Screened Subjects	ES6	Summary of Screening Status and Reasons for Screen Failure		SAC [2]
1.3.	Screened Subjects	NS1	Summary of Number of Subjects by Country and Site ID		SAC [2]
Protocol Deviation					
1.4.	All Subjects	DV1	Summary of Important Protocol Deviations		SAC [2]
Population Analysed					
1.5.	Screened Subjects	SP1	Summary of Study Populations		SAC [2]
Demographics					
1.6.	All Subjects	DM3	Summary of Demographic characteristics	Include BMI	Headline [1] SAC [2]
1.7.	PD	DM3	Summary of Demographic characteristics	Include BMI. Conditional Display	SAC [2]
1.8.	All Subjects	DM11	Summary of Age Ranges	Include only Adult (18-64) and (65-84) years category	SAC [2]

Study Population Tables					
No.	Population	IDSL / Example Shell	Title	Programming Notes	Deliverable [Priority]
1.9.	All Subjects	DM5	Summary of Race and Racial Combinations		SAC [2]
Exposure					
1.10.	All Subjects	EX1	Summary of Exposure Data		SAC [2]

11.10.5. Pharmacodynamic Tables

Efficacy: Tables					
No.	Population	Example Shell	Title	Programming Notes	Deliverable [Priority]
Pharmacodynamic Parameters					
2.1.	PD	LB1	Summary of Exhaled Nitric Oxide Data	Parameter with units, both untransformed and transformed	Headline [1] SAC [2]
2.2.	PD	LB1	Summary of Change from Baseline Exhaled Nitric Oxide Data	Parameter with units for untransformed data	SAC [2]
2.3.	PD	LB1	Summary of Ratio from Baseline Exhaled Nitric Oxide Data	Parameter with units for transformed data	Headline [1] SAC [2]
2.4.	PD	PD_T1	Summary of Repeated Measures Statistical Analysis of Ratio from Baseline Exhaled Nitric Oxide Data after cessation of repeat dose of treatment		Headline [1] SAC [2]
2.5.	PD	PD_T1	Summary of Repeated Measures Statistical Analysis of Ratio from Baseline Exhaled Nitric Oxide Data		SAC [2]
2.6.	PD	LB1	Summary of Spirometry data		SAC [2]
2.7.	PD	LB1	Summary of Change from Baseline in Spirometry data		SAC [2]
2.8.	PD	PD_T1	Summary of Repeated Measures Statistical Analysis of Change from Baseline FEV1 Data		SAC [2]

11.10.6. Pharmacodynamic Figures

Pharmacodynamic: Figures					
No.	Population	IDSL / Example Shell	Title	Programming Notes	Deliverable [Priority]
Pharmacodynamic Parameters					
2.1.	PD	PD_F1	Plot of Individual Subject of Exhaled Nitric Oxide Time-Profile after cessation of repeat dose treatment		SAC [2]
2.2.	PD	PD_F2	Plot of Adjusted Geometric Mean Exhaled Nitric Oxide Ratio from Baseline Time-Profile by Treatment	With confidence intervals taken from repeated measures analysis. Plot to present Day & AM/PM on x-axis and change from baseline ratio on y-axis. One line for each treatment.	Headline [1] SAC [2]
2.3.	PD	PD_F2	Plot of Exhaled Nitric Oxide Ratio from Baseline Treatment Ratios Against Time	With confidence interval taken from repeated measures analyses. Similar to Figure 2.02 but present treatment ratio instead of adjusted mean. Include horizontal line through 1.	SAC [2]
2.4.	PD	PD_F1	Plot of Individual Subject of FEV1 Time-Profile		SAC [2]
2.5.	PD	PD_F2	Plot of Adjusted Mean FEV1 Change from Baseline Time-Profile by Treatment	With confidence interval taken from repeated measures analysis. Present as for FeNO except present for change from baseline instead of change from baseline ratio.	SAC [2]
2.6.	PD	PD_F2	Plot of FEV1 Change from Baseline Treatment Differences Against Time	With confidence intervals taken from repeated measures analysis. Present as for FeNO except present for change from baseline instead of change from baseline ratio.	SAC [2]

11.10.7. Safety Tables

Safety : Tables					
No.	Population	IDSL / Example Shell	Title	Programming Notes	Deliverable [Priority]
Adverse Events					
3.1.	All Subjects	AE1CP	Summary of Adverse Events by System Organ Class and Preferred Term		Headline [1] SAC [2]
3.2.	All Subjects	AE1CP	Summary of All Drug-Related Adverse Events by System Organ Class and Preferred Term		SAC [2]
3.3.	All Subjects	AE1CP	Summary of AEs Leading to Permanent Discontinuation of Study Drug or Withdrawal from Study		SAC [2]

11.10.8. Biomarker Tables

Biomarker Tables					
No.	Population	IDSL / Example Shell	Title	Programming Notes	Deliverable [Priority]
Biomarker parameter					
4.1.	All Subjects	LB1	Summary of Biomarker Data		SAC [2]
4.2.	All Subjects	LB1	Summary of Change from Baseline Biomarker Data		SAC [2]

